2.0 OBJECTIVE(S)/SPECIFIC AIMS

Purpose and specific aims of the study.

Informal caregivers, typically family members or friends, provide more than half of the care needed for the 5.7 million cancer survivors in the United States, often with negative health consequences. At least 30% of survivors and their caregivers report psychological distress (depression and anxiety) and such distress may interfere with optimal symptom management. This study will support both members of the survivor-caregiver dyad in the management of the survivor's cancer- and treatment-related symptoms and the dyad's psychological distress.

Design: We will use the sequential multiple assignment randomized trial (SMART) design, a newer adaptive design. The SMART moves beyond a traditional RCT to a precision approach to determine the right treatment at the right dose with the right sequence for the right survivor-caregiver dyad. We will use two evidence-based interventions: Symptom Management and Survivorship Handbook (SMSH) and Telephone Interpersonal Counseling (TIP-C). While we have established the overall efficacy of these interventions, but individuals differ in responses. When an intervention does not initially work, clinic logic is to either extend the timeframe or prescribe a different intervention. Yet, such alternatives are seldom tested nor evidence-based. However, they will be in this study.

Sample: We will enroll 298 survivors with elevated depression or anxiety who are undergoing chemotherapy or targeted therapy for a solid tumor and their 298 caregivers.

Procedure: Dyads will be initially randomized to SMSH alone or TIP-C +SMSH. If the survivor's elevated depression or anxiety does not respond to SMSH alone by week 4, dyads will be re-randomized to continue with SMSH to give it more time or to TIP-C+SMSH. Outcome data will be collected at baseline, weeks 13 (post-intervention) and 17 (follow-up). Assessments during weeks 1-12 will document changes in symptoms, intervention receipt, enactment and fidelity.

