Specific aims: **1)** Determine if dyads in the TIP-C+SMSH as compared to the SMSH alone group created by the first randomization will have: a) lower depression, anxiety, and summed severity of 13 other symptoms at weeks 1-12, 13, and 17 (primary outcomes); b) lower use of healthcare services (hospitalizations, urgent care or emergency department [ED] visits) during 17 weeks (secondary outcomes); c) greater self-efficacy, social support, and lower caregiver burden during weeks 13 and 17 (potential mediators). **2)** Among nonresponders to the SMSH alone after 4 weeks, determine if dyads assigned to TIP-C+SMSH as compared to the SMSH alone group created by the second randomization will have better primary and secondary outcomes and potential mediators at weeks 5-12, 13, and 17. **3)** Test the interdependence in survivor's and caregiver's primary and secondary outcomes. **4)** Determine which characteristics of the dyad are associated with responses to the SMSH alone during weeks 1-4 and optimal outcomes for the dyad during weeks 1-12, 13 and 17 so as to determine tailoring variables for the decision rules of individualized sequencing of interventions. Findings will be used to improve symptom management and reduce distress in survivor-caregiver dyads.

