
Design. We selected the SMART design (Figure 1) for this study over alternative designs (e.g., implementation designs) because the SMART design allows a precision or personalized approach to determine the right treatment at the right dose with the right sequence for the right survivor-caregiver dyad. SMART designs, although newer, show promise in developing the sequences of evidence-based interventions for more efficient and individualized patient- and caregiver-centered care. We will use findings from this study to create an algorithm for clinically meaningful decision making about symptom management for survivors and their caregivers to be tested in future implementation/dissemination studies. We will recruit 298 cancer survivors undergoing chemotherapy, targeted therapy, or hormonal therapy for a solid tumor at the NCI designated University of Arizona Comprehensive Cancer Center (UACC, Tucson and Phoenix locations) and at Arizona community oncology settings. The survivors will be screened for moderate or severe depression and/or anxiety prior to enrollment and identify the informal caregivers who will participate in the study. Following enrollment, informed consent and baseline interview of both survivor and caregiver, the dyad will be randomly assigned to either: 1) SMSH alone or 2) TIP-C+SMSH for 8 weeks followed by continued SMSH alone for 4 weeks. During 12 weeks following initial randomization, all participants will receive weekly telephone contacts to assess symptoms, deliver the assigned intervention and assess its enactment and fidelity. After the initial 4 weeks in the SMSH alone group, the survivor’s response to the intervention will be determined. If the survivor responds (defined as a reduced score on depression and/or anxiety) (See C9a. Primary Outcomes), the dyad will continue with the SMSH alone for 8 more weeks. If the survivor is a non-responder (defined as no improvement or a worsening score for depression and/or anxiety), the dyad will be re-randomized to either continue with SMSH alone for 8 more weeks, or add 8 weeks of TIP-C. The rationale for using the survivor’s response as the criterion for re-randomization is from the extensive evidence of interdependence in survivor and caregiver outcomes presented, and on the caregiver’s focus on the survivor’s outcomes. The rationale for timing of the assessment of response and re-randomization to add the TIP-C intervention after 4 weeks is based on past testing of the SMSH,^{15,16,30} where median time to response on psychological distress ranged from 14 to 24 days. Post-intervention and follow-up telephone assessments are at weeks 13 and 17.

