summed severity of other symptoms at weeks 1-12, 13, and 17, and lower unscheduled health services use, higher self-efficacy and social support, and lower caregiver burden at weeks 13 and 17 as compared to those initially randomized to the SMSH alone. This hypothesis will be tested using statistical model #1 that relates repeated measures of the survivor or caregiver outcome y (one at a time) to the group assignment variable xx_1 , outcome at baseline xx_2 , time entered as a class variable to model potentially non-linear patterns, and other covariates. For normally distributed outcomes, this model will be fit as a linear mixed effects model (LME). Generalized linear mixed effects (GLME) modeling will be used if outcome is not normally distributed and cannot be normalized using transformations. For health service use, statistical model #1 will be implemented as a GLME model with Poisson distributed errors, or as a zero-inflated Poisson or negative Binomial model based on the distribution of the counts of different health services uses. Each type of health services use (e.g., hospitalizations, ED visits) will be analyzed separately. The explanatory variables including study group will be evaluated as predictors of zero inflation (whether or not the count is zero), and also as predictors of the magnitude of the count when it is not zero. The main effects of the group variable xx_1 will be tested.

Aim 2, Hypothesis 2: Dyads where survivors do not respond to the SMSH alone during weeks 1-4 and have TIP-C added during weeks 5-12, will report lower depression, anxiety, and summed severity of other symptoms at weeks 5-12, 13, and 17, and lower unscheduled health services use, higher self-efficacy and social support, and lower caregiver burden at weeks 13 and 17 as compared to those who are re-randomized to continue with the SMSH alone. The strategy described under the analyses for Aim 1 will be implemented for the repeated outcome measures during weeks 5-12 and weeks 13 and 17 that will be related to group assignment from the second randomization, symptom severity during week 4, time, and covariates.

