9.0 STUDY TIMELINE

List of all parameters and required intervals for observations, measurement of outcomes, intervention and intervals at which it is given.

Table 3 represents the timeline of the project over the 4 years. Table 4 represents the specific schedule of events for the project.

| Table 3: Timeline of the Project | Year 1 | | | | Year 2 | | | | Year 3 | | | | Year 4 | | | | |
|--|-----------|---|---|---|--------|---|---|---|--------|---|---|---|--------|---|---|---|---|
| | Quarters: | 1 | 2 | 3 | 4 | 1 | 2 | 3 | 4 | 1 | 2 | 3 | 4 | 1 | 2 | 3 | 4 |
| IRB approval, update manuals, hire/train staff | X | X | | | | | | | | | | | | | | | |
| Enroll subjects; deliver intervention; collect | | | X | X | X | X | X | X | X | X | X | X | X | X | X | X | |
| Complete survivor health record audits | | | X | X | X | X | X | X | X | X | X | X | X | X | X | X | |
| Set up/conduct analyses; annual/final reports | X | X | | X | | X | X | | | X | X | X | X | X | X | X | X |

Table 4 IRB #: 1804501501

PI: [name]

Schedule Of Events: Improving Informal Caregivers' and Cancer Survivors' Psychological Dis

| Study Item, Service, or Activity NOTES: | Timepoint NOTES: | Screening | Baseline (wk 0) | Weeks 2-4 | Weeks 2-12 | Follow-up (wk 13) | Follow-up (wk 17) |
|--|------------------|-----------|-----------------|-----------|------------|-------------------|-------------------|
| Study Item, Service, or Activity | | | | | | | |
| Inclusion / Exclusion Criteria | | X | | | | | |
| Consent and PHI Auth Signed | | X | | | | | |
| Enroll participant, enter into the queue for baseline via telephone | | | X | | | | |
| Telephone participant to do the baseline or reschedule based on their preference | | | X | | | | |
| Randomize participant post baseline into SMSH or SMSH+ TIP-C Intervention | | | X | | | | |
| Mail study welcome letter, Symptom Management Handbook | | | X | | | | |
| Intervention delivery via telephone | | | | X | | | |
| Rerandomized if survivor is not responding (SMSH only) | | | | X | | | |
| Intervention delivery via telephone (those initially randomized to TIP-C stop TIP-C at week 8; continue with SMSH) | | | | | X | | |
| Follow-up assessment via telephone | | | | | | X | X |
| Follow-up assessment via telephone | | | | | | | |
| Satisfaction and Debriefing via telephone | | | | | | | X |
| Participant is mailed a thank you letter and gift card to thank them for their time | | | X | | | | X |

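### For the weekly GSDS outcomes, the hypotheses claim benefit at weeks 13 and 17 but the plan tests only a time-averaged group effect, which can be positive when nothing is left at those weeks

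*Combined protocol and SAP*

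**What the plan says.** Section 8.0 (repeated in Section 5.0, Analytic Methods) states Hypothesis 1 for depression, anxiety and "summed severity of other symptoms at weeks 1-12, 13, and 17". Model #1 contains the group variable, the baseline outcome, "time entered as a class variable to model potentially non-linear patterns, and other covariates". The stated test is: "The main effects of the group variable xx_1 will be tested". Aim 2 applies the same strategy to "repeated outcome measures during weeks 5-12 and weeks 13 and 17 that will be related to group assignment from the second randomization". No group-by-time term, no contrast at week 13 or week 17 and no within-dyad covariance structure is named.

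Section 2.0 labels week 13 post-intervention and week 17 follow-up. Section 6.0 derives the GSDS depression and anxiety ratings and the sum of the 13 other symptoms at every weekly call and at the interviews. PROMIS depression and anxiety, also listed under primary outcomes, are collected only at baseline and weeks 13 and 17.

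The first-stage combined arm receives "TIP-C+SMSH for 8 weeks followed by continued SMSH alone for 4 weeks" (Section 5.0), and Table 4 in Section 9.0 confirms this: "those initially randomized to TIP-C stop TIP-C at week 8; continue with SMSH". Non-responders in the SMSH arm may start TIP-C after week 4.

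**The concern.** Entering time as a class variable frees the shape of the common time course. It does not let the difference between groups change over time. Without an interaction, the group coefficient is one weighted average of the occasion-specific differences, and for the weekly GSDS outcomes most of those occasions come before week 13. A significant main effect could therefore be reported as support for a hypothesis that names weeks 13 and 17 when the groups no longer differ there.

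A constant group effect is also hard to square with the Aim 1 design, because TIP-C exposure in the two arms changes at weeks 5, 9 and 13.

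**Working it through.** **Inputs.** From Section 4.0: 172 v 60 dyads (Aim 1), 60 v 60 (Aim 2), d = 0.39 raised to 0.54 for 10 repeated measures, correlations 0.36-0.77, two-sided 0.05. From Section 8.0: weeks 1-12, 13 and 17 (14 occasions) and weeks 5-12, 13 and 17 (10 occasions).

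**1. The plan's own power.** The standard error of a standardised difference is √(1/n1 + 1/n2).
- Aim 1: √(1/172 + 1/60) = 0.150; 0.54/0.150 = 3.60; power 0.95, as the plan states.
- Aim 2: √(2/60) = 0.183; 0.54/0.183 = 2.96; power 0.83 (noncentral t), consistent with 0.80 or greater.

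**2. Weight on weeks 13 and 17.** With no group-by-time term, the generalised least squares weights are V⁻¹1/(1′V⁻¹1), where V is the correlation matrix of the occasions.
- Exchangeable: equal weights, so 2/14 = 14% (Aim 1) and 2/10 = 20% (Aim 2).
- AR(1), lag-1 r from 0.36 to 0.77: 22-34% and 30-41%. Reading the plan's range of pairwise correlations as lag-1 values is an assumption.

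**3. Chance of p < 0.05 when the effect is zero at weeks 13 and 17.** Scale d = 0.54 by the weight on the weeks that carry the effect, then use the noncentral t.

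| Scenario | Aim 1 | Aim 2 |
|---|---|---|
| Exchangeable, effect at every week to 12 | 0.54 × 12/14 = 0.463: 0.87 | 0.54 × 8/10 = 0.432: 0.65 |
| Exchangeable, effect starts one week later | 0.54 × 11/14 = 0.424: 0.80 | 0.54 × 7/10 = 0.378: 0.54 |
| AR(1) weights, r = 0.36, later start | 0.54 × 0.680 = 0.367: 0.68 | 0.54 × 0.575 = 0.310: 0.39 |
| AR(1) weights, r = 0.77, later start | 0.54 × 0.470 = 0.254: 0.39 | 0.54 × 0.361 = 0.195: 0.19 |

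**4. Sensitivity.** The 0.54 already embeds some covariance. Starting from 0.39 instead, and letting the assumed covariance set both weights and variance, gives for r = 0.36 to 0.77:
- exchangeable, effect at every week to 12: 0.94 to 0.71 (Aim 1) and 0.75 to 0.48 (Aim 2);
- AR(1), later start: about 1.00 to 0.57 and 0.83 to 0.23.

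If the Aim 1 effect is confined to weeks 2-8, ending with TIP-C, the average is 0.54 × 7/14 = 0.27 and the chance is 0.43 (exchangeable).

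**5. Is a constant Aim 1 effect plausible?** The plan expects 120 non-responders re-randomised 1:1, so 60 of 172 comparator dyads (35%) receive TIP-C.

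| Weeks | TIP-C-first arm | SMSH-first arm |
|---|---|---|
| 1-4 | TIP-C | none |
| 5-8 | TIP-C | about 35% on TIP-C |
| 9-12 | TIP-C ended | about 35% on TIP-C |
| 13, 17 | TIP-C ended | TIP-C ended |

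Four different exposure contrasts share one coefficient. The Aim 1 probabilities in steps 3 and 4 ignore this dilution from week 5 and are therefore upper-end.

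**6. Power of a single-week contrast at d = 0.39.** Aim 1: 0.39/0.150 = 2.60, power 0.74. Aim 2: 0.39/0.183 = 2.14, power 0.56. At 1:1, power of 0.80 would need 104 per group.

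**The case against.** The best defence is that a time-averaged effect is a coherent reading of hypotheses that name 14 and 10 occasions, and it is the quantity that Section 4.0 powers. That stands, and it is why the average should remain the overall test. It does not license a statement about week 13 or week 17 in particular.

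Four stronger readings are tempting, and the documents do not support them.

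- *Every hypothesised outcome is dominated by weekly ratings.* PROMIS depression and anxiety, service use, the PROMIS mediators and caregiver burden have post-baseline values only at weeks 13 and 17. Their main effect contains no weekly ratings. It still pools the two weeks, so week 17 is not tested separately. The plan does not say whether GSDS or PROMIS supplies depression and anxiety in model #1, so for those two outcomes the reach of the point depends on that choice. The 13-symptom sum exists only in the GSDS.
- *A vanished effect would certainly be declared.* This is a probability that varies widely with covariance and scenario. An effect that is full to week 12 and exactly zero at week 13 is a stark case, especially in Aim 1, where TIP-C ends at week 8.
- *Durability after TIP-C is a stated objective left untested.* No aim says so. It is an inference from the follow-up label.
- *Early and late TIP-C will be compared at week 13.* The mixed-model analyses for Aims 1 and 2 plan no such comparison. Week 13 is 5 weeks after TIP-C ends in the TIP-C-first arm and 1 week after in the step-up arm. Matching on time since TIP-C (week 13 with week 17) would not repair it, because step-up dyads are selected week-4 non-responders while the TIP-C-first arm is unselected.

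The mediation and Aim 3 models use weeks 13 and 17, but they test indirect and dyadic effects. They are not a stated test of the group difference at those weeks.

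**Conclusion.** The point holds for the weekly GSDS outcomes, most clearly for the 13-symptom sum. The hypotheses claim benefit at weeks 13 and 17, and the only specified test of the group difference is an average in which those weeks carry a minority of the weight under every structure examined. An effect absent at both weeks would often be declared: about 0.80-0.87 in Aim 1 and 0.54-0.65 in Aim 2 under exchangeable correlation on the plan's d = 0.54, and down to about 0.39 and 0.19 with AR(1) weights. These figures assume complete data at the post-attrition sample sizes, a correlation structure that the plan does not specify, and an effect that is zero at both interviews. For interview-only outcomes the narrower point remains that weeks 13 and 17 are pooled. The average test itself is not invalid; what needs correcting is what may be concluded from it.

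**What to change.** 1. Add group by time to model #1 and to the Aim 2 model.
2. Keep the time-averaged group effect as the overall, powered test, and call it that in the hypotheses and reports.
3. Pre-specify the group contrasts at week 13 and at week 17 as supporting estimates with confidence intervals. For Aim 1 also give weeks 1-4 and weeks 5-12. Base any statement about weeks 13 and 17 on these contrasts.
4. State which instrument, GSDS or PROMIS, supplies depression and anxiety in these models.
5. Do not set TIP-C-first at week 13 beside step-up at week 17.

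The cost is one model term and a few contrasts from data already collected. The contrasts are less precise than the average: at d = 0.39, power is about 0.74 (Aim 1) and 0.56 (Aim 2) for a single week. The plan should say that they are not powered at 0.80. Treating them as supporting estimates avoids adding confirmatory tests across three primary outcomes and two dyad members, which matters because the multiplicity adjustment in Section 8.0 is stated only for exploratory analyses.

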Symptom burden in cancer survivors. Physical and psychological symptoms are aggravated while cancer survivors are in treatment.^{103,104} Survivors' symptom burden¹⁰⁵⁻¹¹² is often the primary reason for altering or stopping chemotherapy^{113,114} leading to suboptimal treatment at the very least,¹¹⁵⁻¹¹⁷ and life threatening recurrence or metastasis at the extreme.^{118,119} The prevalence of specific symptoms (e.g., fatigue, pain, depression, anxiety, disturbed sleep, nausea and vomiting, neuropathy)¹²⁰⁻¹²⁵ varies by cancer diagnosis, treatment type, gender, ethnicity and age,^{98,99} variables that will be empirically tested as potential tailoring factors in decision rules that will be formulated in this research. The number of symptoms reported by cancer survivors can be as high as 14.^{126,127} Approximately 30% of cancer survivors report psychological distress (depression and anxiety). Major depression occurs in approximately 16%, and subthreshold depressive disorders occur in 22% of cancer survivors during treatment.²⁸ These prevalence rates are about 3 times higher than in the general population. Even when depression and anxiety do not meet threshold for clinical diagnoses, these symptoms are still associated with significant health impairments, yet are highly treatable,^{128,129} and will be in this trial, potentially saving healthcare costs and improving outcomes. Further, in our past studies, Latinas with breast cancer reported a higher number and more symptom burden/distress than did non-Hispanic white women with similar diagnoses.³¹ Therefore, we will enroll an ethnically diverse sample (includes 30% Hispanic/Latino participants) in this trial to address a significant symptom management need. Given the increasing population of Hispanic cancer survivors, providing and testing an intervention in the participant's primary language could have national significance. A series of longitudinal studies¹³⁰⁻¹³³ including those conducted by this team^{130,131}, found an association between increasing symptom prevalence and poorer physical and emotional functioning. Our team's past work¹³⁴ and that of others¹³⁵ documented the associations between reductions in symptoms and lower number of hospitalizations, office and ED visits.¹⁰ The proposed interventions are significant because they will address the multiple symptoms experienced by survivors during treatment and the associated health care service use.

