Response will be assessed using the depression and anxiety items of the GSDS administered during weekly calls to survivors. Based on the inclusion criteria and established and validated symptom cut points,²²⁴ survivors will enter with moderate or severe depression and/or anxiety (one symptom or both). The cut-points are anchored in how much symptoms are distressing the participant by interfering with enjoyment of life, social relationships, and general daily activities. Participants indicate the severity/distress from 1 to 10. For depression, the mild category corresponds to a severity score of 1, the moderate category corresponds to scores 2-3, and scores of 4-10 fall into the severe category. For anxiety, the mild category is

severity of 1-3, the moderate category corresponds to scores 4-5, and the severe category is 6-10. Survivors who start at severe or moderate on depression and/or anxiety symptoms at intake and end at a lower category by the week 4 observation will be called **responders to the intervention**.²²⁸ If a symptom was mild at intake, symptom response would not be applicable. Because responders demonstrate substantial improvement anchored to symptom distress after 4 weeks, responders will continue with the SMSH only intervention for another 8 weeks. **Non-responders to the intervention** are survivors who do not respond on either or both symptoms.^{224,251,252} Non-responding survivors and their caregivers will be re-randomized to either continue with the SMSH alone for 8 weeks to give it additional time or add TIP-C for 8 weeks to rigorously test the value added by the more intensive intervention in Aim 2. Total intervention time is 12 weeks.

Caregivers' and survivors' depression and anxiety. PROMIS-short forms 8: depression and anxiety²⁵³⁻²⁵⁶ will be administered at baseline, 13 and 17 week telephone interviews to provide greater detail and precision in the measurement of these outcomes, as compared to single GSDS items administered in weekly calls. We chose 8-item short forms to minimize respondent burden while maintaining measurement precision.

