Exploratory Aim 4. The dyadic characteristics of responders will be compared to those of non-responders using t-tests, chi-square or Fisher's exact tests. Characteristics found to differ, along with mediators and other covariates listed in section C9d will be further considered as potential future tailoring variables. The decision rule (dd_1, dd_2) specifying the first and second intervention to achieve optimal outcome will be using the Qlearning optimization method^{258,270-272} implemented in SAS PROC QLEARN.^{273,274} The Q-learning algorithm proceeds backwards from the last decision to the first. Two Q-functions will be considered. The function $QQ_2(HH_2) = EE[YY_2|HH_2]$ is the expectation of the second stage outcome YY_2 given history after 2 stages, denoted by HH_2 : dyadic characteristics, outcomes observed during weeks 1-12, 13 and 17, and interventions received. The function $QQ_1(HH_1) = EE[YY_1 + \max QQ_2(HH_2)]$ uses history through the first intervention stage HH_1 . The conditional expectations in the Q-functions will be estimated from regression analyses for the primary outcomes, and the optimal decision rules will be found using backward induction by maximizing these functions.^{275,276} The product of this analysis will be identification of tailoring variables to operationalize the decision rules of selecting the optimal first intervention and switching from SMSH alone to TIP-C+SMSH. These personalized decision rules can then undergo testing in a future confirmatory RCT.

Potential Difficulties/Limitations and Alternative Approaches

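### Aim 4's responder comparison cannot adjust for intake severity, although the drop needed to count as a responder depends on the starting score

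*Combined protocol and SAP*

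**What the plan says.** Section 2.0 gives as the opening part of Aim 4: "Determine which characteristics of the dyad are associated with responses to the SMSH alone during weeks 1-4".

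The method appears in the same words under Exploratory Aim 4 in Sections 5.0 and 8.0: "The dyadic characteristics of responders will be compared to those of non-responders using t-tests, chi-square". Fisher's exact test is the third option named there. The next sentence reads: "Characteristics found to differ, along with mediators and other covariates listed in section C9d will be further considered as potential future tailoring variables". Q-learning regressions on the primary outcomes follow, and the resulting decision rules are meant for a later confirmatory trial.

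Section 6.0 defines response as ending week 4 in a lower severity category than at intake. For depression a score of 1 is mild, "the moderate category corresponds to scores 2-3, and scores of 4-10 fall into the severe category". Anxiety has its own cut-offs: 1 to 3 counts as mild, 4 or 5 as moderate, and 6 or more as severe. A non-responder is someone who fails on one symptom or on both. The text does not settle whether a survivor elevated on both must improve on both. Section 5.0 (Design) instead describes response as any reduced score on depression and/or anxiety, and refers onward for detail.

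**The concern.** Aims 1 and 2 adjust for the baseline or week-4 value, and the mediation models adjust for baseline. The Aim 4 screen has no such adjustment, although its outcome is tied to the starting score by construction. A survivor who goes from depression 4 to 3 has responded; one who goes from 10 to 4 has not.

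The confounding is foreseeable. Section 1.0 says that symptom prevalence varies by diagnosis, treatment type, gender, ethnicity and age, and names these as candidate tailoring factors. It also reports that "Latinas with breast cancer reported a higher number and more symptom burden/distress than did non-Hispanic white women", and about 30% of the sample is to be Hispanic/Latino. A characteristic that only tracks starting severity could be reported as a marker of poor response to SMSH. A characteristic with a real benefit could be masked if its carriers start higher.

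**Working it through.** **1. The group in question.** Section 4.0 expects 120 non-responders at a 30% response rate: 120 / 0.70 = 171.4, rounded up to 172, as stated. That leaves 172 − 120 = 52 responders. Aim 4 has no power figure.

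**2. Drop needed for response under Section 6.0.** The drop is the starting score minus the top of the next lower category: s − 3 for severe and s − 1 for moderate depression; s − 5 for severe and s − 3 for moderate anxiety.

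| Start | 2 | 3 | 4 | 5 | 6 | 7 | 8 | 9 | 10 |
|---|---|---|---|---|---|---|---|---|---|
| Depression | 1 | 2 | 1 | 2 | 3 | 4 | 5 | 6 | 7 |
| Anxiety | – | – | 1 | 2 | 1 | 2 | 3 | 4 | 5 |

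The relation is not monotone: depression 3 needs a larger drop than 4, and anxiety 5 a larger drop than 6.

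**3. What this does to the chance of response.** Assume that every survivor's drop has mean 1 and SD 2 whatever the start. For a required drop k, with a half-point continuity correction, P = 1 − Φ((k − 0.5 − 1)/2).
- Depression 4 (k = 1): 1 − Φ(−0.25) = 0.60
- Depression 6 (k = 3): 1 − Φ(0.75) = 0.23
- Depression 8 (k = 5): 1 − Φ(1.75) = 0.04

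**4. Effect on the tests, by simulation.** From the plan: n = 172, about 30% response, and the Section 6.0 categories. The two-sided 0.05 level is the one the plan uses in its power calculation. Assumed: latent means 3.5 (depression) and 4.5 (anxiety), SD 2.4, correlation between symptoms about 0.5, residual SD of change 2, 600 runs per setting. A false flag is a significant result for a trait with no effect on change; r is the trait's correlation with starting severity. The real trait is assumed to be worth 0.6 points per SD. If every elevated symptom must respond:

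| Slope of week-4 on intake score | 1.0 (no regression to the mean) | 0.7 | 0.5 |
|---|---|---|---|
| False flags, t-test, r = 0.2 | 12% | 9% | 6% |
| False flags, t-test, r = 0.3 | 22% | 14% | 8% |
| False flags, t-test, r = 0.5 | 50% | 27% | 14% |
| Real trait detected, r = +0.3, t-test | 35% | 58% | 64% |
| Real trait detected, r = +0.3, adjusted logistic | 80% | 83% | 79% |

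If any one symptom suffices, the t-test's false flags are 5-7% throughout, and it detects the real trait in 74-88% of runs. With logistic adjustment for starting category and required drop, false flags are 3-8% in every setting. Monte Carlo error is about 1-2 points. Some logistic fits gave convergence warnings, so those figures are approximate.

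A separate simulation (n = 172, 30% response, assumed scores, r = 0.3) used ANCOVA on the week-4 score as the comparator:
- Every elevated symptom must respond: false flags 7-18% unadjusted against 3-5%; detection of a real trait 49-71% against about 95%.
- Any one symptom suffices: false flags 5-7% unadjusted; detection 77-91% against 93-94%.

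The two sets together give the 7-22% range at r = 0.3.

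**5. Does anything else bring in intake severity?**
- The covariate list in Section 8.0 does not name intake depression or anxiety.
- The general statement there on adjusting for baseline outcome values addresses imperfect randomisation. Responder versus non-responder is not a randomised contrast, and a t-test or chi-square test takes no covariate.
- The false-discovery step controls multiplicity; it does not remove confounding.
- Q-learning models outcomes in order to choose interventions; it does not estimate which characteristics go with response to SMSH alone.

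**The case against.** - **The screen is not the only gate.** A reader might infer that useful tailoring variables will be lost. The documents do not support that: mediators and listed covariates are considered further whatever the screen shows. This stands, and it confines the problem to the stated question about response to SMSH alone.
- **The response rule is ambiguous.** A reader might take it as settled that a survivor elevated on both symptoms must improve on both. The text does not settle it, and if one symptom suffices the false-flag rate is near nominal. This stands. Response would still depend on the starting score. Under Section 5.0's any-reduction wording, the distance effect would largely vanish.
- **The upper rates need unlikely inputs.** The 50% figure needs r = 0.5 and no regression to the mean. Survivors are selected for elevated single-item scores, and Section 4.0 gives repeated-measure correlations of 0.36 to 0.77; unless the spread of scores grows, that implies slopes below 1. This stands.
- **Per-test rates leave out the planned false-discovery step.** In a simulation with one confounded trait among 15 tested (an assumed number) and every elevated symptom required to respond, raw flags of 7-28% fell to 0.6-6% after Benjamini-Hochberg. Several confounded traits together would raise this. The point stands for the size of the problem, but the surviving flags are still biased.
- **Missing real traits is not general.** At zero correlation with severity, detection is 80-85% unadjusted against 83-84% adjusted. At r = −0.3 it is 93-98% unadjusted, so such a trait is over-detected. Nor is it shown that the yes/no outcome discards most of the information.
- **A marginal association is still an association.** A trait that goes with non-response because its carriers start worse does describe who meets the re-randomisation trigger. That is a reason to keep the table as description, not to read it as differential benefit from SMSH.

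**Conclusion.** The point holds in a limited form. That the named tests cannot adjust for intake severity, and that the required drop runs from 1 to 7 points (depression) or 1 to 5 (anxiety), follows from the text. That characteristics can be wrongly flagged or masked follows from these two facts. How often is not determined by the documents: it depends on the spread of starting scores, regression to the mean, the trait's link to severity, and the reading of the response rule. At an assumed correlation of 0.3, the per-test range is about 7-22% before false-discovery adjustment if every elevated symptom must respond, and about 5-7% if any one suffices.

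A reader might infer that such errors are certain, or that higher starting scores always mean poorer response. Neither is supported. No primary result is affected, and Aim 4 is exploratory. The change is still worthwhile because it is cheap and improves the answer to a stated aim. Under the any-one-symptom reading, the gain comes mainly from analysing the score and not from the adjustment.

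**What to change.** In Exploratory Aim 4, in both Sections 5.0 and 8.0, and within the group first randomised to SMSH alone:

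1. Regress the week-4 depression and anxiety scores on each characteristic, adjusting for intake depression, intake anxiety and the number of elevated symptoms.
2. If yes/no response is kept, use logistic regression adjusted for starting category and distance to the category boundary on each symptom. With about 52 responders, keep these models small and check convergence.
3. Apply the planned false-discovery adjustment to the regression results.
4. Keep the unadjusted responder/non-responder table as description only.

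Separately, reconcile Section 5.0 (any reduced score) with Section 6.0 (a lower category), and state how a survivor elevated on both symptoms is classified.

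The cost is analysis-plan wording and a few regressions on data already collected; trial conduct does not change for the analysis part. The downside is that results come as score points or adjusted odds ratios and not as a simple two-group table.
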